Subject Selection Criteria	
Inclusion Criteria
 
 Men or women aged 18 years or older Cardiomyopathy patients 
 -Patients presenting for CMR with the clinical diagnosis of hypertrophic cardiomyopathy based on left ventricular wall thickness of at least ≥ 15 mm in the absence of any other cardiac or systemic cause of hypertrophy -Patients presenting for CMR with the clinical diagnosis of idiopathic dilated cardiomyopathy based upon left ventricular ejection fraction $\leq 40\%$, LV end-diastolic diameter ≥ 55 mm or left ventricular end-systolic diameter ≤ 45 mm, and the absence of coronary stenoses on angiography. Control patients with atypical chest pain 
 -Patients presenting for CMR evaluation of chest pain but without evidence of obstructive coronary artery disease either by coronary angiography or stress testing. 
Exclusion Criteria
 
 Decompensated heart failure or hemodynamic instability Prior coronary revascularization (PCI or CABG) or myocardial infarction (as evidenced by previously elevated CPK-MB or troponin levels) Accelerating angina or unstable angina Inability to physically tolerate MRI or implanted objects that are MRI incompatible Inability to provide written informed consent obtained at time of study enrollment. Severe claustrophobia Advanced heart block or sinus node dysfunction Hypersensitivity or allergic reaction to regadenoson or adenosine Hypotension Active bronchospasm or history of hospitalization due to bronchospasm History of seizures Recent cerebrovascular accident Use of dipyridamole within the last 5 days Contraindication to aminophylline Severe renal insufficiency with estimated glomerular filtration rate < 30 ml/min/ 1.73 m² Pregnant or nursing
Length of Study	
Projected duration of enrollment: 1-1.5 years
 
Projected duration of analysis and manuscript preparation: 0.5-1 year
 
Total study duration: ~2.5 years

Primary Endpoint	The primary endpoint will be the prevalence of MVD by CMR. The hypothesis is that global perfusion reserve will be significantly lower in patients with hypertrophic cardiomyopathy and idiopathic dilated cardiomyopathy than in controls with atypical chest pain. We also anticipate that differences in prevalence of MVD between the cardiomyopathy groups will be observed.

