We propose to study the prevalence of MVD in patients with hypertrophic cardiomyopathy and idiopathic dilated cardiomyopathy compared to controls with atypical chest pain. MVD will be assessed by CS-CMR and will be defined by presence of global perfusion reserve <2.0 , which is a standard threshold used in prior studies.² Based on our initial observations, we believe our measurement of MVD will clearly distinguish between patients with cardiomyopathy and control patients with atypical chest pain, who have normal coronary arteries and no evidence of ischemia. The prevalence of MVD will be greater than 50% for both HCM and IDCM, but will be different between patients with hypertrophic cardiomyopathy and idiopathic dilated cardiomyopathy.

Secondary Objectives

To demonstrate the generalizability of global perfusion reserve as measure of MVD, we will compare the CS-CMR measurement of global perfusion reserve with regadenoson versus that adenosine to demonstrate that they are similar. Specifically, the global perfusion reserve in all participants receiving regadenoson will be compared to those receiving adenosine using a two sample t-test. We will also explore whether differences within the subgroups are present (e.g. controls receiving regadenoson vs controls receiving adenosine; HCM patients receiving regadenoson vs HCM patients receiving adenosine; IDCM patients receiving regadenoson vs IDCM receiving adenosine). However, given the relatively small numbers, we expect the within subgroup comparisons to be mainly for the generation of hypotheses for subsequent studies.

Additionally, based on our initial observations, we anticipate that the presence and severity of MVD will be dependent on different morphological and functional characteristics in HCM and IDCM. Specifically we will examine:

- (1) the relationship between MVD and scarring
- (2) the relationship between MVD and regional perfusion defects
- (3) the relationship between MVD and LV morphologic characteristics (mass, volume, ejection fraction)

As a tertiary objective, we will also estimate the amount of interstitial fibrosis present in the myocardium of patients HCM and IDCM, compared to controls. Interstitial fibrosis will be estimated using MODified Look-Locker Inversion-recovery sequence (MOLLI) sequence, which is performed prior to and after contrast administration. We will attempt to discern if an association exists between MVD and increases in interstitial fibrosis.

Methods

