Patient Selection

We will recruit patients referred to the DCMRC with a documented history of hypertrophic cardiomyopathy or idiopathic dilated cardiomyopathy. Those agreeing to consent will be enrolled and undergo the multifaceted CMR protocol (**Figure 3**). Patients with history of coronary artery disease will be excluded.

To serve as controls, we will recruit patients referred for CMR for atypical chest pain. Only patients with low Framingham Risk (10% or less CHD risk at 10 years) and no history of CAD will be considered for recruitment. Controls will be excluded if they have evidence of obstructive coronary artery disease either by coronary angiography or stress testing.

Other Exclusion Criteria

Patients will also be excluded for the following reasons:

- Decompensated heart failure or hemodynamic instability
- Prior coronary revascularization (PCI or CABG) or myocardial infarction (as evidenced by elevated CPK-MB or troponin levels)
- Accelerating angina or unstable angina
- Inability to physically tolerate MRI or implanted objects that are MRI incompatible
- Inability to provide written informed consent obtained at time of study enrollment.
- Severe claustrophobia
- Advanced heart block or sinus node dysfunction
- Hypersensitivity or allergic reaction to regadenoson or adenosine
- Hypotension
- Active bronchospasm or history of hospitalization due to bronchospasm
- History of seizures
- Recent cerebrovascular accident
- Use of dipyridamole within the last 5 days
- Contraindication to aminophylline
- Hypersensitivity or allergic reaction to gadolinium contrast media
- Severe renal insufficiency with estimated glomerular filtration rate <30 ml/min/ 1.73 m²
- If they are pregnant or nursing

A detailed clinical history will be performed in all patients at the time of CMR. Information including age, gender, symptomatology, blood pressure, weight, height, and cardiac risk factors will be recorded. 12-lead ECGs will be obtained in all. Blood will be drawn for measurement of creatinine (point of care) and hematocrit. In women of childbearing potential, a serum HCG will be drawn.

Study Specific Procedures

Upon agreeing to participate in the study, subjects will be randomized to receive regadenoson or adenosine.

CMR Overview

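### The two alternative size limits for IDCM entry point in opposite directions: one is a floor on ventricular diameter, the other a ceiling

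*Combined protocol and SAP*

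**What the plan says.** The only place that gives diameters is the Study Synopsis, Subject Selection Criteria. There the "clinical diagnosis of idiopathic dilated cardiomyopathy based upon left ventricular ejection fraction" ≤ 40%, with the size limits and angiographic condition "LV end-diastolic diameter ≥ 55 mm or left ventricular end-systolic diameter ≤ 45 mm, and the absence of coronary stenoses on angiography".

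Methods, Patient Selection gives no measurements: "We will recruit patients referred to the DCMRC with a documented history of hypertrophic cardiomyopathy or idiopathic dilated cardiomyopathy". Nothing there, or elsewhere in the document, explains or corrects the direction of either limit.

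Hypothesis and Aims, Primary Objective then makes predictions about the group so defined: "The prevalence of MVD will be greater than 50% for both HCM and IDCM". It also predicts that prevalence will differ between the two cardiomyopathies.

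**The concern.** Two limits joined by 'or' as alternative evidence of the same condition should point the same way. Here "LV end-diastolic diameter ≥ 55 mm" selects larger ventricles and "left ventricular end-systolic diameter ≤ 45 mm" selects smaller ones. As written, a patient can satisfy a test for a dilated ventricle by having a small end-systolic chamber.

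Three things are at stake.

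- **Who is in the group.** IDCM is one of the two cardiomyopathy groups in the primary prevalence analysis, with 30 patients planned. Each patient wrongly admitted or excluded carries 1/30, about 3.3 percentage points, of the estimated prevalence.
- **What is analysed.** The secondary objectives relate microvascular dysfunction (MVD) to LV volume and ejection fraction. An entry rule that works the wrong way on chamber size acts on a variable closely tied to these.
- **Reproducibility.** A report quoting this definition would describe a population that another centre could not sensibly reproduce.

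**Working it through.** The plan gives no figure to reproduce; the check is one of logic, followed by an illustration.

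**Inputs** (Study Synopsis, Subject Selection Criteria): end-diastolic diameter (EDD) ≥ 55 mm; end-systolic diameter (ESD) ≤ 45 mm; connector 'or'; LVEF ≤ 40%. The only added fact is that ESD does not exceed EDD.

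**Step 1: what the size condition admits.** The condition is EDD ≥ 55 or ESD ≤ 45.

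| EDD | Size condition met? | Reason |
|---|---|---|
| ≤ 45 mm | Always | ESD ≤ EDD ≤ 45, so the end-systolic limit is met |
| Above 45 and below 55 mm | Only if ESD ≤ 45 mm | The end-diastolic limit fails, so the end-systolic limit decides |
| ≥ 55 mm | Always | The end-diastolic limit is met |

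The condition can therefore reject only in the middle band, and there it rejects the larger end-systolic chambers. At EDD 50 mm, for example, ESD 44 mm passes and ESD 47 mm fails. This step needs no formula for ejection fraction.

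**Step 2: does LVEF ≤ 40% remove the problem?** Take two ventricles, EDD/ESD 50/44 mm and 54/48 mm. The document does not convert diameters to LVEF, so two formulas are assumed.

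- Cube: LVEF = 1 − (ESD/EDD)³.
  - 50/44: 1 − 0.681 = 31.9%.
  - 54/48: 1 − 0.702 = 29.8%.
- Teichholz: V = 7D³/(2.4 + D), D in cm, and LVEF = 1 − V(ESD)/V(EDD).
  - 50/44: 25.8%.
  - 54/48: 23.9%.

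All four values are ≤ 40%, so only the size condition separates the two. The 50/44 mm ventricle qualifies. The 54/48 mm ventricle is larger in both phases and has the lower LVEF, yet meets neither limit.

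**Step 3: whom does the end-systolic limit bring in?** Set ESD = 45 mm and LVEF = 40% and solve for the largest compatible EDD.

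- Cube: 45/0.6^(1/3) = 53.4 mm.
- Teichholz, solved numerically: 56.1 mm.
- Short-axis area only, LVEF = 1 − (ESD/EDD)²: 45/0.6^(1/2) = 58.1 mm.

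Under the cube formula, every patient with LVEF ≤ 40% who meets the end-systolic limit lies below the protocol's own 55 mm limit. Under the other two, the compatible range extends only 1.1 mm and 3.1 mm above it.

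**The case against.** The strongest reply has five parts.

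1. **It may be a misread character.** The text was extracted by a program, and an extraction error would not be an error in the plan. This stands as a caution: the original page must be checked first. Other signs nearby (wall thickness ≥ 15 mm, LVEF ≤ 40%, glomerular filtration rate < 30) read plausibly, so there is no positive sign of a misreading.
2. **The criterion can be satisfied.** The limits concern different cardiac phases and are joined by 'or', so a patient may meet either or both. That is true; the conflict is one of direction and intent, not impossibility.
3. **Other conditions protect the group.** Patients arrive with a clinical diagnosis and must also have LVEF ≤ 40% and no coronary stenoses. This limits the practical effect, and a very small ventricle in someone already diagnosed should be rare. But the Synopsis bases the diagnosis on these same measurements, so the diagnosis is not a fully independent safeguard.
4. **The examples use assumed formulas.** The study itself calculates LVEF from traced short-axis cine volumes (Image Analysis). This is fair: Steps 2 and 3 are illustrations only. Step 1 does not depend on them.
5. **The sentence could be read as a three-way 'or'.** Then the 54/48 mm ventricle would enter on LVEF. That is the less natural reading and does not rescue the ceiling: an end-systolic diameter ≤ 45 mm would then count as sufficient whatever the LVEF.

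**Conclusion.** The concern holds for the text as supplied. The two size limits run in opposite directions, no other section corrects them, and read literally the rule can admit a smaller ventricle while turning away a larger one. A sign slip is the likeliest explanation, but the document does not state the intended limit.

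The extent of the defect is exact: the size condition is always met at EDD ≤ 45 mm and at ≥ 55 mm, and fails only between them when ESD is > 45 mm. This rests on ESD not exceeding EDD, on the natural reading of the sentence, and on the sign being the same on the original page.

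The effect on results is not known. Neither the number of patients affected nor any shift in MVD prevalence can be derived from the document. The MVD definition (global perfusion reserve < 2.0) and the sample-size calculation are not affected. The point should be fixed because it defines a primary-analysis group and the remedy is so cheap.

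**What to change.** 1. Check the end-systolic sign against the original page and against the source definition that the investigators used.
2. If the sign is as read here, reconcile the two limits so that both denote dilatation. The investigators must supply the intended limit; this review does not propose one. Punctuate the sentence so that it is clear LVEF, the size condition and the absence of stenoses are all required, if that is the intent.
3. Review the eligibility of any IDCM participant who met the end-systolic limit but not the end-diastolic one. If screening records exist, look also for patients turned away because they met neither limit.
4. Optionally, point from Methods, Patient Selection to the corrected definition. This is editorial only.

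The cost is one clarified sentence and an eligibility check confined to a subset of at most 30 planned IDCM participants. No analysis or sample size changes.

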Secondary Endpoints	The secondary endpoints will include 
• A comparison of CMR global perfusion reserve using regadenoson versus adenosine.• A comparison of the correlation coefficients between the extent of MVD and other CMR metrics, including myocardial scar size, extent of regional perfusion defects, and morphological and function characteristics such as LV mass, LVEF, and LV volume.
----------------------------	--

Scientific Rationale

Coronary microvascular dysfunction (MVD) has been implicated as an important marker of cardiac risk and has been thought to directly contribute to the pathogenesis of a wide variety of cardiomyopathies.^{1,2} For instance, MVD is believed to cause ischemia (with reduction in coronary flow reserve) in patients with hypertrophic cardiomyopathy (HCM) despite the presence of angiographically normal epicardial coronary arteries. The implication is that MVD in HCM may lead to the ventricular arrhythmias, sudden death, and heart failure. Similarly, patients with idiopathic dilated cardiomyopathy (IDCM) have blunted coronary flow reserve, which appears to be independently associated with poor prognosis.

Several etiologic mechanisms have been proposed to explain the occurrence of MVD, including structural and functional abnormalities¹:

- (a) increased microvascular resistance due to reduced vascular luminal caliber.
- (b) reduced density of microvessels associated with replacement scarring.
- (c) inappropriate vasoconstrictor responses.
- (d) inadequate vasodilator responses.

Unfortunately, these mechanisms are difficult to study in humans since no technique currently allows the direct visualization of the coronary microcirculation *in vivo*. Thus, MVD has been largely studied using non-invasive imaging techniques, such as positron emission tomography (PET) or single photon emitted computed tomography (SPECT).

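### Comparing correlation coefficients can show different MVD relationships in HCM and IDCM when the slopes are equal, because entry criteria restrict LVEF in IDCM directly and LV volume and mass indirectly

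*Combined protocol and SAP*

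**What the plan says.** The Secondary Endpoints row of the Study Synopsis lists "A comparison of the correlation coefficients between the extent of MVD and other CMR metrics". The metrics are scar size, extent of regional perfusion defects, and "morphological and function characteristics such as LV mass, LVEF, and LV volume", five in all. Hypothesis and Aims, Secondary Objectives, gives the purpose: the investigators expect that "the presence and severity of MVD will be dependent on different morphological and functional characteristics in HCM and IDCM". The contrast of interest is therefore between the two cardiomyopathy groups.

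The Subject Selection Criteria define those groups:
- HCM requires "left ventricular wall thickness of at least ≥ 15 mm", with no limit on LVEF or cavity size.
- IDCM rests on "the clinical diagnosis of idiopathic dilated cardiomyopathy based upon left ventricular ejection fraction" of 40% or less, together with "LV end-diastolic diameter ≥ 55 mm or left ventricular end-systolic diameter ≤ 45 mm" and the absence of coronary stenoses.

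Statistical Methods contains only the sample size for MVD prevalence. The documents do not say whether coefficients are compared between groups or between metrics, whether groups are pooled, which correlation is used, or how two coefficients are to be compared. They mention no slope, interaction term or allowance for differing ranges.

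**The concern.** A correlation mixes two things: how steeply global perfusion reserve changes with the metric, and how widely the metric varies in the patients studied. The second is partly set by the entry criteria, and these differ between groups. If LVEF is confined to a narrow band in one group, its correlation with perfusion reserve falls there even when the dependence on LVEF is the same in both. The reverse can also happen: a steeper slope over a narrower range can give the same correlation and hide a real difference.

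Pooling the groups does not help. The pooled coefficient then includes the between-group differences in LVEF and in perfusion reserve, which partly reflect how patients were chosen.

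At stake is the secondary conclusion that the two diseases have different MVD phenotypes. The Pilot Data section already interprets nine patients (five HCM, four IDCM) in terms of weaker and stronger relationships, so the planned comparison is likely to be read in the same way.

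**Working it through.** **The plan's own figure.** None is given for this analysis. The only power statement (71%, 25 per group) concerns MVD prevalence and does not bear on this point.

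**Inputs from the documents.** 30 HCM and 30 IDCM patients (Planned Enrollment); 25 per group in the sample size paragraph; alpha 0.05, taken here as two-sided.

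**Assumptions.** The documents give no SD for any metric. I let u be the metric's SD in the narrower group divided by its SD in the wider group, and r the correlation in the wider group. Both are varied. Slope and residual SD are set equal in the two groups, and the relationship is linear.

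**Step 1: correlation in the narrower group.** With metric and outcome scaled to SD 1 in the wider group, the slope is r and the residual variance is 1 − r². In the narrower group

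r₂ = r·u / √(1 − r² + r²u²).

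- r = 0.5, u = 0.75: 0.375 / √(0.75 + 0.1406) = 0.40
- r = 0.5, u = 0.5: 0.25 / √(0.75 + 0.0625) = 0.28
- r = 0.5, u = 1/3: 0.1667 / √(0.75 + 0.0278) = 0.19
- r = 0.7, u = 0.5: 0.35 / √(0.51 + 0.1225) = 0.44

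**Step 2: how often equal slopes are declared different.** Simulated normal data, at least 20,000 trials per setting, 30 per group. The Fisher-z statistic is |atanh(r₁) − atanh(r₂)| / √(2/(n − 3)), compared with 1.96.

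| r in wider group | u = 1 | u = 0.75 | u = 0.5 | u = 1/3 |
|---|---|---|---|---|
| 0.3 | 5% | 6% | 9% | 12% |
| 0.5 | 5% | 8% | 17% | 27% |
| 0.7 | 5% | 11% | 31% | 53% |

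The metric-by-group interaction test stays at about 5% in every cell. At 25 per group and u = 0.5, the Fisher-z rates are about 15% (r = 0.5) and 26% (r = 0.7).

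**Step 3: a real difference hidden.** If the slope doubles while the SD halves, slope × SD is unchanged, so r₂ = r. The correlation comparison then rejects at only about 5%, although the slopes differ twofold.

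**Step 4: pooling.** With two equal groups, the pooled covariance is the within-group covariance plus one quarter of the product of the two between-group mean differences (metric and perfusion reserve). A pooled correlation can therefore be non-zero when both within-group slopes are zero.

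**Step 5: limits of the slope test.** At r = 0.5 and u = 0.5, doubling the residual SD in the narrower group moves the ordinary interaction test to about 9%; halving it moves the test to about 2%. Separate residual variances with adjusted degrees of freedom restore about 5% in both cases. Power is low: in the same setting with equal residual SDs, a narrower-group slope of zero, or of twice the wider-group slope, is detected in about 27% of trials.

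**The case against.** The strongest reply is that none of these error rates belongs to the plan. It names no test for comparing correlations, and no section gives the spread of LVEF, mass or volume. If the spreads are equal there is no distortion, and at u = 0.75 it is mild. That stands, and it is why the rates are illustrations. One could try to fix u by truncating an assumed LVEF distribution at 40%, but that compares IDCM with a hypothetical unselected version of itself. The comparison needed is with HCM, whose LVEF spread is not given. Even which group is narrower cannot be read from the documents.

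A reader might also infer that the whole endpoint is compromised by the entry criteria. The documents do not support that. Scar size and perfusion defects are not entry criteria; for them the argument applies only if their spreads differ, which the contrasting scar burden in the two Figure 2 patients hints at but cannot establish. Wall thickness is only a proxy for LV mass. The IDCM diameter criterion joins two limits by an or, and they run in opposite directions (end-diastolic at least 55 mm, end-systolic at most 45 mm). How far LV volume is restricted is therefore unclear, and that wording needs to be reconciled.

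A third reply is that strength of association, not slope, may be the target. A different correlation is then a real feature of the patients enrolled, but it cannot be interpreted without the metric's range. Comparing metrics within one group does not escape the problem either, because the criteria restrict some metrics and not others.

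Finally, slopes have their own conditions. They are unaffected by selection on the metric itself only if the relationship is linear. Selection through a related variable, such as diameter or wall thickness, is harmless only if that variable adds nothing once the metric is known.

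**Conclusion.** The concern holds in a conditional form: differing ranges can be mistaken for differing relationships. The case is direct for LVEF in IDCM, indirect for LV volume and LV mass, and conditional on unequal spreads for scar size and perfusion defects.

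The false-difference rates in the table rest on a Fisher-z comparison, linearity, equal residual SDs and assumed SD ratios. It would go too far to say that the phenotype conclusion will be an artefact, or that the planned analysis has a 17% error rate; the documents fix neither the test nor the spreads. What they do establish is that the statistic chosen does not isolate the dependence that the objective asks about. The primary endpoint is unaffected. The point deserves action because the remedy costs almost nothing.

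**What to change.** State in Statistical Methods that the contrast of interest is HCM versus IDCM. Then, for each of the five metrics:
- Regress global perfusion reserve (log-transformed if its distribution calls for it) on metric, group and metric-by-group interaction, with standard errors that allow unequal residual variance.
- Report within-group slopes with 95% confidence intervals, and the metric's SD and range in each group. Inspect the fit for non-linearity, particularly where the groups' ranges overlap little.
- Keep within-group correlations as descriptive. Do not pool groups without adjusting for group.

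Present the results as exploratory across the five metrics, since the interaction test has low power at 30 per group and a non-significant result would not show equal dependence.

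The cost is analysis wording only. Every quantity needed is already produced under Image Analysis, and no added patients, scans or visits are required.

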The CMR methodology and analysis to be used are fully described in the references. The entire scan procedure and scan time should take around 45 minutes. A cardiologist or fellow will supervise the scan, assess/triage patients, and initiate treatment if needed. A schematic of the imaging procedure is shown in **Figure 3**.

1. Standard Scout images of the heart leading to double oblique horizontal long axis view (4-Chamber) of the heart
2. Cine Image of the horizontal long axis view of the heart
3. Prescribed double oblique short axis view of the heart with first slice at the insertion points of the mitral valve in diastole.
4. Cine images of the short axis of the left ventricle from the base to and including the apex for entire LV coverage.

[figure not shown]

Figure 3. Multifaceted CMR examination

5. Cine images of the long axis views of the heart (2 chamber, 3 chamber, 4 chamber).
6. MOLLI images will be obtained prior contrast administration.
7. Coronary sinus imaging at rest as described in Figure 1.
8. Patients and controls will receive either (a) regadenoson (0.4 mg IV) injection over 10 seconds followed by saline flush or (b) adenosine $140 \mu\text{g}\cdot\text{kg}^{-1}\cdot\text{min}^{-1}$ x 3 minutes. During the injection or infusion, the participants will be monitored (continuous ECG and blood pressure monitoring) for 3-4 minutes. Half of the participants will receive Regadenoson, while the remainder will receive adenosine. Any serious adverse reactions during or after vasodilator stress will be recorded.
9. Stress perfusion images of 4-5 short axis slices (basal, mid, and apical) per heart beat for 60 heart beats beginning after 1-1.5 minutes after the regadenoson injection.
10. Bolus contrast injection of 0.1 mmol/kg of gadolinium contrast (gadoteridol or gadoteric acid) followed at 30 cc of saline flush beginning beginning after 1-1.5 minutes after regadenoson administration or after 2 minutes of adenosine infusion.
11. Coronary sinus imaging during stress (Figure 1).
12. In those receiving regadenoson, aminophylline (100 mg IV) will be administered over 30-60 seconds after completion of coronary sinus imaging. If bronchospasm is noted, participants will be treated with inhaled albuterol metered dose inhaler.
13. After a 15 minutes wait period, rest perfusion images of 4-5 short axis slices per heart beat for 60 heart beats using the identical imaging location and parameters as the stress perfusion images.

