For calculation of left ventricular mass, volume, and ejection fraction, endocardial borders on the stack of short-axis cine images in end diastole and end systole, and the epicardial borders in end diastole, will be traced using planimetry. End diastolic volume (EDV) and end systolic volume (ESV) are calculated from the product of the area end-diastole and end systole respectively and the thickness of the imaged slice (10 mm). Left ventricular ejection fraction (LVEF) is calculated using the following formula:

$$\text{LVEF} = \frac{\text{end diastolic volume} - \text{end systolic volume}}{\text{end diastolic volume}}$$

Left ventricular mass is calculated by subtracting endocardial from epicardial volumes and multiplying by myocardial density (1.05 g/cm³).

The amount of interstitial fibrosis will be estimated by calculating the extracellular volume fraction from the MOLLI images.

The myocardial extracellular volume fraction (ECF) is calculated from the following formula:

$$ECF_{\text{myo}} = [1 - \text{hematocrit}] * \Delta R1_{\text{myo}} / \Delta R1_{\text{blood}}$$

where $\Delta R1 = (R1_{\text{post-contrast}}) - (R1_{\text{pre-contrast}})$ for myocardium or blood, respectively, and $R1 = 1/T1$. ECF values above that of a normal population are considered abnormal (elevated) and are inferred to represent increased fibrosis.

All image analyses will be performed blinded to patient identity and clinical characteristics.

Statistical Methods

Sample size Determination

The determination of sample size is based upon the primary aim of the study to assess the prevalence of MVD in subtypes of cardiomyopathy. Using a cutoff value of ≥ 2.0 as normal for global perfusion reserve, our pilot data demonstrates that MVD is present in approximately 70% patients with HCM, whereas none of the 3 controls had MVD. Samples sizes of 25 in each group (HCM and IDCM) will provide 71% power to detect a difference of 25% in the presence of MVD at $\alpha=0.05$.

Expected Start Date / Length of Enrollment

Immediate start date once protocol is approved. Given rate of enrollment of pilot data, we anticipate enrollment will be completed in 12-18 months.

Data Handling and Record Keeping

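### The plan aims to show that regadenoson and adenosine give similar perfusion reserve, but the test it names can only detect a difference, and no margin or confidence-interval rule is given

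*Combined protocol and SAP*

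**What the plan says.** The document is a combined protocol with a short Statistical Methods section. The comparison of stress agents appears in these places.

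- **Hypothesis and Aims, Secondary Objectives.** The purpose is to support the generalisability of global perfusion reserve by comparing it "with regadenoson versus that adenosine to demonstrate that they are similar". The analysis is that "the global perfusion reserve in all participants receiving regadenoson will be compared to those receiving adenosine using a two sample t-test". Agent comparisons within controls, HCM and IDCM are also planned, with the caveat that "we expect the within subgroup comparisons to be mainly for the generation of hypotheses for subsequent studies".
- **Study Synopsis, Secondary Endpoints.** The wording is more neutral: "A comparison of CMR global perfusion reserve using regadenoson versus adenosine".
- **CMR Overview, step 8.** "Half of the participants will receive Regadenoson, while the remainder will receive adenosine". Study Specific Procedures states that the agent is randomised; stratification by diagnosis is not described.
- **Hypothesis and Aims, Primary Objective.** The expectation is that "our measurement of MVD will clearly distinguish between patients with cardiomyopathy and control patients with atypical chest pain".
- **Statistical Methods, Sample size Determination.** "The determination of sample size is based upon the primary aim of the study". Nothing is said there about the agent comparison.

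Planned enrolment is 30 HCM, 30 IDCM and 15 controls.

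**The concern.** The aim and the test point in opposite directions. The null hypothesis of a two-sample t-test is equality, so the test can supply evidence of a difference but not of similarity. Failure to reject becomes more likely as the data get noisier, so imprecision would favour the conclusion the investigators hope to reach. The plan does not say that p>0.05 will be read as similar. That reading is an inference, but a natural one, because no other criterion is offered.

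A second, lesser point concerns precision. The overall test pools HCM, IDCM and controls with no diagnosis term, although the plan expects the measurement to separate cardiomyopathy from controls. The spread between diagnoses therefore enters the error term.

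At stake is the claim that perfusion reserve carries over from one agent to the other. MVD is defined by a single cutoff, reserve below 2.0, whichever agent is used, so an unsupported claim of similarity would lend unearned support to using that cutoff across agents.

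**Working it through.** **The plan's own figures.** There are none for this comparison. The only power statement, 71% with 25 per group and a 25-point difference in MVD prevalence, belongs to the primary aim. The arcsine formula comes close to it for 70% versus 95% (the 95% is inferred): Φ(0.708 × √(25/2) − 1.96) = 70.7%. It has no bearing on the agent comparison.

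**Inputs from the document.** Total 30 + 30 + 15 = 75, half to each agent, so 38 versus 37 and 73 degrees of freedom. I use two-sided alpha 0.05; the document states 0.05 for the primary aim only.

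**Assumed inputs.** The document gives no SD, group means or relevant difference for perfusion reserve. I take an SD of 0.5 to 0.9 and differences or margins of 0.3 to 0.5 reserve units.

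**Step 1: precision.** The 95% CI half-width is t(0.975, 73) × SD × √(1/38 + 1/37) = 1.993 × 0.231 × SD = 0.46 SD.

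**Step 2: how often a real difference gives p>0.05.** Noncentral t, with noncentrality equal to difference / (0.231 × SD):

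| SD | 95% half-width | p>0.05, true difference 0.3 | p>0.05, true difference 0.4 |
|---|---|---|---|
| 0.5 | 0.230 | 27% | 7% |
| 0.6 | 0.276 | 43% | 19% |
| 0.75 | 0.345 | 60% | 38% |
| 0.9 | 0.414 | 70% | 52% |

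In SD units, with no SD assumed, a true difference of 0.5 SD is missed 43% of the time, and 80% power is reached only at about 0.66 SD.

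By contrast, a rule that the 90% CI must lie wholly inside a margin (two one-sided 5% tests) calls a true difference equal to the margin similar at most 5% of the time, whatever the SD.

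**Step 3: cost of ignoring diagnosis.** Weights are 30/75, 30/75 and 15/75, that is 0.4, 0.4 and 0.2. The assumed within-group SD is 0.6 (variance 0.36).

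- HCM/IDCM/control means 1.6/1.8/2.4: overall mean 1.84, between-group variance 0.086, pooled SD √(0.36 + 0.086) = 0.67, ratio 1.11.
- Means 1.6/1.8/2.8: overall mean 1.92, between-group variance 0.202, pooled SD √(0.36 + 0.202) = 0.75, ratio 1.25.

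The unadjusted interval is thus about 11% to 25% wider than the adjusted one.

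**Step 4: subgroup comparisons.** By the same half-width formula for SD 0.5 to 0.9, 15 versus 15 (HCM or IDCM) gives 0.37 to 0.67, and 8 versus 7 (controls) gives 0.56 to 1.01. These are too wide to settle similarity.

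**Step 5: what an equivalence rule could achieve.** Power of the 90% CI rule when the agents are identical (400,000 simulated trials per cell):

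| Analysis and SD | Margin 0.3 | Margin 0.4 | Margin 0.5 |
|---|---|---|---|
| Adjusted, 0.6 (71 df) | 38% | 78% | 95% |
| Unadjusted, 0.67 | 22% | 64% | 88% |
| Unadjusted, 0.75 | 8% | 48% | 78% |

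Without the adjustment contrast, an SD of 0.5 gives 65%, 93% and 99%, and an SD of 0.9 gives 0.2%, 21% and 54%.

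**The case against.** The best defence is that nothing planned is invalid. The agent is randomised, so an unadjusted t-test is a fair comparison, and a mean difference with its interval follows from the same data. The plan never says it will equate non-significance with similarity. The synopsis speaks only of comparing the agents, so the Secondary Objectives wording may simply be loose. Sizing a study on its primary aim alone is ordinary practice, and the subgroup comparisons are already labelled exploratory. Finally, the size of the problem rests on assumed SDs: at SD 0.5 a difference of 0.4 is missed only 7% of the time.

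Much of this is fair, and it limits the point. Omitting diagnosis costs precision and does not bias the comparison. The absence of a separate sample size is not an error in itself. The miss rates are illustrative, and the document cannot show which end of the range applies.

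The core is not answered. The objective is stated as showing similarity, the next sentence specifies the test that serves it, and no section supplies a rule by which similarity could be concluded. That mismatch does not depend on any assumed SD. If the wording is merely loose, rewording it is one of the two remedies below.

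**Conclusion.** The concern holds. The specified test cannot support the conclusion that the objective names, and no other part of the document repairs this. That follows from the text and is firm.

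The practical size is conditional. For an assumed SD of 0.5 to 0.9 with 38 versus 37 participants, non-significance would accompany a true difference of 0.3 in 27% to 70% of trials. The gain from adjusting for diagnosis likewise depends on the illustrative group means.

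This should be fixed, but it concerns a secondary objective and leaves the primary prevalence analysis unaffected.

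**What to change.** Replace the pooled t-test with a linear model for global perfusion reserve containing agent and diagnostic group (HCM, IDCM, control), and report the agent difference with its confidence interval. Then choose one of the following.

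1. **Keep the similarity claim.** Prespecify a margin and justify it. Conclude similarity only if the 90% CI lies inside the margin; otherwise report the result as inconclusive, with the interval.
2. **Restate the objective** as estimating the agent difference with its CI, and drop "to demonstrate that they are similar". This would bring the section into line with the synopsis.

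The cost is a few sentences of analysis text, plus one margin to justify under option 1. No extra participants or scans are needed. The drawback of option 1 is that it may well be inconclusive even if the agents are identical, as the power table shows. If 0.3 is the difference that matters, option 2 is the more realistic choice. Stratifying the randomisation list by diagnosis, if that is not already intended, is an optional low-cost addition.
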